6.1.2 Dose Adjustments of MIRCERA® and ESA

6.1.2.1 Patients Not Currently Treated with an ESA

Dose adjustments of MIRCERA® and reference ESA treatments may be made until the individual target Hb level is obtained (Hb range of 10 – 12 g/dL) [3, 4, 10-14].

The MIRCERA® dose may be increased by approximately 25% (or 50% according to approved label in the country) of the previous dose if the rate of rise in Hb is less than 1.0 g/dL over a month. Further increases of approximately 25% (or 50% according to approved label in the country) may be made at monthly intervals until the individual target Hb level is obtained.

If the rate of rise in Hb is greater than 2 g/dL in one month or if the Hb level is increasing and approaching 12 g/dL, the MIRCERA® dose is to be reduced by approximately 25% (or 50% according to approved label in the country). If the Hb level continues to increase, therapy should be interrupted until the hemoglobin level begins to decrease, at which point therapy should be restarted at a MIRCERA® dose approximately 25% below the previously administered dose.

Dose adjustments should not be made more frequently than once a month.

If the desired Hb concentration is reached for the individual patient, MIRCERA® may be administered once monthly using the dose equal to twice the previous once every two weeks dose.

Dose adjustment for the reference ESA should be done according to the approved label [10, 11, 12, 13].

6.1.2.2 Patients Treated with an ESA

If a dose adjustment is required to maintain the Hb concentration of 10 -12 g/dL, the MIRCERA® monthly dose may be increased by approximately 25% [3, 4, 14].

If the rate of rise in Hb is greater than 2 g/dL over a month or if the Hb level is increasing and approaching 12 g/dL, the MIRCERA® dose is to be reduced by approximately 25% (or 50% according to approved label in the country). If the Hb level continues to increase, MIRCERA® therapy should be interrupted until the Hb level begins to decrease, at which point therapy should be restarted at a MIRCERA® dose approximately 25% below the previously administered dose. MIRCERA® Dose adjustments should not be made more frequently than once a month.

Since the treatment experience is limited in patients on peritoneal dialysis, regular Hb monitoring and strict adherence to dose adjustment guidance is recommended in these patients.

Dose adjustment for the reference ESA should be done according to the approved label [10, 11, 12, 13].

6.2 Preparation and Administration of MIRCERA® and Comparator[s]

MIRCERA® in PFS will be administered by sc or iv injection. MIRCERA® sc injection sites are the abdomen, thigh or arm. If two sc injections are necessary (volume of injection >1 mL), then the second injection should be performed on the opposite side of the body (e.g., abdomen right/abdomen left).

In order to assure study drug administration and documentation, MIRCERA® and reference ESAs must be administered by an appropriately trained health care professional; self-administration of study medications is allowed only under the supervision of a health care professional.

Home administration will be allowed when no study visits are planned or blood samples are to be taken. Home administration may be performed under the supervision of appropriately trained medical staff aware of the study procedures.

The reference ESAs will be administered to the patients according to approved labels.

After injection, all empty blisters/medication boxes with patient identification must be retained and made available for the Roche Monitor to check at each visit (see section 6.5).

6.3 Formulation, Packaging and Labeling

Local packaging in some countries may be different.

6.3.1 Formulation of MIRCERA®

MIRCERA® will be provided in sterile single-use injectable solution in PFS containing 0.3 mL or 0.6 mL solution respectively. The MIRCERA® solution contains the following excipients: sodium dihydrogen phosphate monohydrate, sodium sulphate, mannitol (E421), methionine, poloxamer 188, water for injections.

The injectable solution is available in the following strengths (in µg):

PFS	30	50	75	100	120	150	200	250	360
-----	----	----	----	-----	-----	-----	-----	-----	-----

The PFS should be stored in a refrigerator at 2-8°C and protected from the light. The investigational site is responsible for maintaining a daily temperature log of this refrigerator.

6.3.2 Packaging and Labeling of MIRCERA®

Study medication will be packaged and provided in an open label fashion. *It will be supplied with either study-specific labels or as commercially available product with additional labeling, if required by national legislation.* Each syringe will be available in an individual blister with a needle for sc or iv administration. The package labels will include the following information: protocol number, study drug name, strength, lot number, re-tests date/used by (as per local guidelines), patient number, administration date and safety precautions for clinical trials.

6.3.3 Formulation of Reference ESAs

The formulation of the reference ESAs (Aranesp®, Nespo®, Aranest®, Eprex®, Epogen®, Epopen®, Erypo®, NeoRecormon® and Recormon®) will be according to approved labels [10, 11, 12, 13].

Reference ESAs will be handled and administered according to approved labels. The drug should be stored in a refrigerator (2°C – 8°C). The investigational site is responsible for maintaining a daily temperature log of any refrigerator used for the reference ESAs storage.

6.3.4 Packaging and Labeling of Reference ESAs

The reference ESAs used for the study will be provided either by Roche or by individual study centers, depending on country specifications.

For study centers/countries where reference ESAs will be supplied by Roche, reference ESAs will be packed and labeled according to local specifications, in an open fashion. *It will be supplied with either study-specific labels or as commercially available product with additional labeling, if required by national legislation.* Each PFS will be available blistered in an individual box.

6.4 Blinding and Unblinding

Not applicable, the study is open-label.

6.5 Assessment of Compliance

Accountability and subject compliance will be assessed by maintaining adequate drug dispensing and return records.

A Drug Inventory/Dispensing Log provided by Roche must be kept current and should contain the following information at a minimum:

- the identification of the subject to whom the study medication was dispensed
- the date[s], quantity of the study medication dispensed *to* the subject
- the initials of the person confirming administration of the study medication
- the date[s] and quantity of the study medication returned *by* the subject

The inventory *and dispensing logs* must be available for ongoing inspection by the Monitor. After injection, all empty blisters of PFS of MIRCERA® or reference ESA will be kept in a container or in the medication box and will be made available for the Roche Monitor to check at each visit. All supplies, including partially used, expired and unused or empty containers and dispensing logs, must be kept at the study site and *copies of the inventory and dispensing logs will be retrieved by the Roche Monitor* at the end of the study.

In case of home administrations, for assessment of compliance, subjects will be asked to return empty blisters/medication boxes with the drug administration records at each study visit.

6.6 Destruction of the MIRCERA®/Reference ESAs

The unused, partially used or expired MIRCERA®/reference ESA PFS provided by the Sponsor may be destroyed at the site or at the supplying depot following the current Roche and local Standard Operating Procedures as applicable.

Local or institutional regulations may require immediate destruction of used MIRCERA®/reference ESA PFS for safety reasons. In these cases, it may be acceptable for investigational site staff to destroy dispensed MIRCERA®/reference ESA PFS before a monitoring inspection provided that source document verification is performed on the remaining inventory and reconciled against the documentation of quantity shipped, dispensed, returned and destroyed. Written authorization must be obtained from the sponsor at study start up before destruction.

Written documentation of destruction must contain the following:

- Identity [batch numbers or subject numbers] of MIRCERA®/reference ESA [if applicable] destroyed
- Quantity of MIRCERA®/reference ESA PFS destroyed
- Date of destruction (*date discarded in designated hazardous container for destruction*)
- Method of destruction (*the site must provide the Sponsor with documentation of their institutional policy and procedures for handling and disposing of drugs*)
- Name and signature of responsible person [or company] who *discarded the investigational products[s] in a hazardous container for destruction*

7. SAFETY INSTRUCTIONS AND GUIDANCE

7.1 Adverse Events (AEs) and Laboratory Abnormalities

7.1.1 Clinical AEs

According to the International Conference of Harmonization [ICH], an AE is any untoward medical occurrence in a patient or clinical investigation subject administered a pharmaceutical product and which does not necessarily have a causal relationship with this treatment. An AE can therefore be any unfavorable and unintended sign [including an abnormal laboratory finding], symptom, or disease temporally associated with the use of a medicinal [investigational] product, whether or not considered related to the medicinal [investigational] product. Pre-existing conditions which worsen during a study are to be reported as AEs.

Clinical AEs encountered during the randomized treatment period will be recorded on an AE eform of the eCRF (see figure in [Appendix 1](#)).

Kidney transplantation and routine diagnostic procedures/tests are not considered AEs and should therefore not be recorded on an AE eform of the eCRF.

In patients not on dialysis, start of dialysis should not be considered as an AE and should be recorded on a specific eCRF form. If the worsening of kidney function justifying dialysis is faster than expected, the worsening of kidney function may be recorded as an AE term and the dialysis procedure should be recorded in the treatment section of the AE eform.

Cardiac laboratory tests (e.g., troponin I, troponin T) will be assessed in case of suspected MI.

Coagulation laboratory tests (e.g., prothrombin time (PT) or INR, thrombin time (TT), partial thromboplastin time (PTT)) will be assessed in case of bleeding adverse events.

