4.3.3 Dialysis

For patients on dialysis, dialysis modality (HD or PD), PD type, the number of HD sessions per week, the type of vascular access for HD, time since first dialysis and dialysis adequacy assessments should be documented in the eCRF.

Dialysis treatment should be performed according to current guidelines [8, 9].

If a patient not on dialysis requires dialysis (HD or PD) due to worsening of renal function, CrCl/GFR should be determined (using either the abbreviated MDRD or the Cockcroft-Gault equations; see [Appendix 3](#)). For the continuation of the study, pre- and post-dialysis blood pressure should be measured at each visit. The start of dialysis and dialysis modality should be documented in the dialysis eform of the eCRF.

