5.4.2 Laboratory Assessments during the Treatment Period

Normal ranges for the local study laboratory parameters must be supplied to Roche before the study starts.

The total volume of blood loss for laboratory assessments will be approximately 2-40 mL per visit with safety assessments representing a total of approximately 112 mL per year of participation.

Blood sampling during the study should always be performed before MIRCERA® or ESA administration.

The following laboratory assessments will be performed during the randomized treatment period:

- Hematology:
 - Hb at study visit 1, at monthly visit and at the final visit. Hb will be assessed twice monthly until Hb has stabilized.
 - Platelet count at study visit 1 *and* at monthly visit.
 - Total white blood cell count at study visit 1 *and* every 3 months
- Blood chemistry:
 - CRP every 3 months.
 - Serum albumin, calcium, phosphorus, potassium at study visit 1 *and* every 3 months.
- Iron parameters:
 - Serum ferritin, serum iron, serum transferrin or TIBC, TSAT or percentage of hypochromic RBCs every 3 months.
- Cholesterol, triglycerides, HbA1c, glucose at study visit 1 *and* once a year.
- Anti-erythropoietin antibody determination at study visit 1, once a year and at the final visit.
- Patients on HD: Kt/V or URR will be determined at study visit 1 and every 6 months; patients on PD: the weekly Kt/V at study visit 1, every 6 months (see [Appendix 3](#) for definitions).
- Patients not on dialysis: serum creatinine, creatinine clearance/glomerular filtration rate at study visit 1, every 6 months (CrCl/GFR, estimated with the abbreviated MDRD or the Cockcroft-Gault equations [[Appendix 3](#)]).
- 12-lead ECG recording at study visit 1 before dose administration.

The biological samples for specific parameters (anti-erythropoietin antibody determination) which will be analyzed by central laboratories should be classified, packed and shipped as UN 3373 Biological substance, Category B for dispatch purposes, as required by the international regulations and procedures.

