8.2.6 Other Safety Data Analyses

The safety parameters will be vital signs, AEs and the safety laboratory parameters including iron parameters.

Adverse event data will be presented in frequency tables (overall and by intensity) by body system. In tables showing the overall incidence of adverse events, subjects who experienced the same event on more than one occasion are counted only once in the calculation of the event frequency. Adverse events will be summarized throughout the whole study treatment period and up to 30 days after the last administration of study treatment.

Deaths will be listed and summarized descriptively. Vital signs and laboratory data will be analyzed descriptively and will be assessed for clinically relevant abnormalities as well as changes from baseline. The results of the exploratory statistical analysis of NT-proBNP and troponin T will be reported separately.

Demographic and baseline disease characteristics will be summarized by treatment arm for all randomized patients.

The secondary objectives (incidence of anti-erythropoietin antibody-mediated pure red cell aplasia (PRCA), gastrointestinal bleeding and thromboembolic events), will be analyzed using descriptive statistics and analytical methods such as risk ratios, Cox regression and ANOVA methods.

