Appendix 3 Additional Information on Laboratory/Clinical Assessments

– Creatinine Clearance

GFR can be estimated using either the Cockcroft & Gault formula¹ or the simplified or extended MDRD formulae. In general, the MDRD formulae provide a more accurate estimate of GFR in subjects with reduced renal function, regardless of patient weight².

The abbreviated (also called “four-variable” or “simplified”) MDRD Study equation has been validated to estimate CrCl/GFR in CKD patients^{3,4}. It uses age (years), sex (female vs. non-female), race (African-American vs. non-African-American), and serum creatinine.

Abbreviated MDRD formula²

SI Units

$$\text{GFR} = 186.3 \times (\text{serum creatinine } [\mu\text{mol/L}] \times 0.0113)^{-1.154} \times (\text{age})^{-0.203} \times (0.742 \text{ if female}) \times (1.212 \text{ if African-American})$$

GFR: glomerular filtration rate (mL/min/1.73 m²)
Age (years)

An automatic GFR calculator is available online at the National Kidney Foundation web site: http://www.kidney.org/professionals/kdoqi/gfr_calculator.cfm.

Cockcroft & Gault formula¹

SI Units

$$\text{Cr Clearance (mL/min)} = f \times (140 - \text{age}) \times \text{IBW} / (0.81 \times \text{serum Cr } (\mu\text{mol/L}))$$

f = 1.0 for males and 0.85 for females. Age in years, IBW in kg
IBW (male) = [0.9 x Height (cm)] – 88
IBW (female) = [0.9 x Height (cm)] – 92

¹ Cockcroft DW, Gault MH. Prediction of creatinine clearance from serum creatinine. *Nephron* 1976;16:31-41

² Levey AS, Bosch JP, Breyer Lewis J, Greene T, Rogers N, Roth D & the Modification of Diet in Renal Disease Study Group. A More Accurate Method to Estimate Glomerular Filtration Rate from Serum Creatinine: A New Prediction Equation. *Ann Intern Med.* 1999; 130 (6): 461-470.

³ Levey AS, Greene T, Kusek JW, Beck GJ. A simplified equation to predict glomerular filtration rate from serum creatinine. *J Am Soc Nephrol* 2000;11:155A. abstract.

⁴ Levey AS, Coresh J, Balk E, et al. National Kidney Foundation practice guidelines for chronic kidney disease: evaluation, classification, and stratification. *Ann Intern Med* 2003;139:137-47. [Erratum, *Ann Intern Med* 2003;139:605].

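### For patients not on dialysis at entry, the planned renal safety tables can blur an arm difference: the AE rules conflict, GFR follow-up ends at dialysis, and dialysis start is never analysed

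*Combined protocol and SAP*

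**What the plan says.** Four parts of the protocol bear on renal decline in patients who enter off dialysis.

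- **AE recording, section 7.1.1.** The general rule is "Pre-existing conditions which worsen during a study are to be reported as AEs". The section then makes an exception: "In patients not on dialysis, start of dialysis should not be considered as an AE and should be recorded on a specific eCRF form". For the underlying decline it says "If the worsening of kidney function justifying dialysis is faster than expected, the worsening of kidney function may be recorded as an AE term", and in that case "the dialysis procedure should be recorded in the treatment section of the AE eform". Section 7.1.3 separately asks for any clinically significant, treatment-emergent laboratory abnormality to go on the AE form, for example one that calls for a change of therapy. Section 7.2.1 requires serious events to be reported in either arm. Section 6.4 confirms that the trial is open-label.
- **GFR measurement, section 5.4.2.** "Patients not on dialysis: serum creatinine, creatinine clearance/glomerular filtration rate at study visit 1, every 6 months". Patients on dialysis have Kt/V or URR instead. Either the abbreviated MDRD or the Cockcroft-Gault equation may be used. Appendix 3 gives the first in mL/min/1.73 m² and the second in mL/min, and comments: "In general, the MDRD formulae provide a more accurate estimate of GFR in subjects with reduced renal function".
- **Dialysis start, section 4.3.3.** "The start of dialysis and dialysis modality should be documented in the dialysis eform of the eCRF". The same section asks for a CrCl/GFR determination when dialysis becomes necessary.
- **Analysis, section 8.2.6.** "Vital signs and laboratory data will be analyzed descriptively and will be assessed for clinically relevant abnormalities as well as changes from baseline". The safety parameters listed there are vital signs, AEs and safety laboratory values. Dialysis start is not among them, and it is not an endpoint in section 8.1.

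**The concern.** This is a safety study. Its title names patients not on renal replacement therapy, and the synopsis lists CrCl/GFR as a safety parameter for them. A reader of the final report would look for any arm difference in renal decline in the AE tables and the GFR summary. Each has a weakness that can depend on treatment.

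In the AE tables, whether a decline to dialysis appears can turn on an undefined standard applied by someone who knows the drug, under rules that disagree. Death, MI and stroke go to blinded adjudication (section 10.3); this judgement does not. In the GFR summary, patients drop out of the scheduled measurements because they declined, so an arm with more dialysis starts loses more of its worst values. The record that depends least on judgement about cause or pace, the start of dialysis, is collected but not used.

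**Working it through.** **1. Patients affected.** 0.20 × 2800 = 560, or 280 per arm (sections 3.2 and 4).

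**2. AE rules side by side.** Take one patient whose creatinine rises until dialysis is needed.

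- General rule in 7.1.1: the worsening is an AE.
- Specific rule in 7.1.1: the worsening is optional, and only if judged quicker than anticipated; the dialysis itself is not an AE.
- 7.1.3: if the laboratory change is clinically significant, for example because therapy must change, it should be an AE.

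Two sites could record this patient differently and each cite the protocol.

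**3. What that can do to AE counts.** The documents give no rate of dialysis start, so these inputs are assumed. Let dialysis start in 30% of the reference arm and 40% of the MIRCERA arm: 280 × 0.30 = 84 and 280 × 0.40 = 112. If sites label 30% of reference starts as unexpectedly fast, that gives 84 × 0.30 = 25.2 AEs. A share of 22.5% on MIRCERA gives 112 × 0.225 = 25.2, the same count. With a reference share of 20–50% and a MIRCERA start rate of 36–45%, the equalising share (reference share × 0.30 / MIRCERA start rate) runs from 13.3% to 41.7%.

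**4. What truncation can do to GFR change.** Baseline GFR, slopes and a dialysis threshold are not in the documents. Assumed for illustration: linear decline, dialysis below GFR 10, deaths ignored, mean slopes differing by 2 mL/min per year, and 400,000 simulated patients per arm. The true difference in mean change is 2 × 2 = 4 mL/min at 2 years and 2 × 4 = 8 at 4 years. The last column compares patients still off dialysis.

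| Baseline (SD) | Mean slopes | Slope SD | On dialysis by 4 y | True difference kept at 4 y |
|---|---|---|---|---|
| 20 (6) | −3 / −5 | 2 | 55% / 83% | 52% |
| 20 (6) | −3 / −5 | 3 | 54% / 76% | 42% |
| 20 (6) | −3 / −5 | 4 | 53% / 71% | 38% |
| 25 (8) | −3 / −5 | 3 | 40% / 62% | 54% |
| 20 (6) | −2 / −4 | 3 | 42% / 66% | 46% |

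Re-runs agree within about one point: 61–83% kept at 2 years and 37–54% at 4 years. In absolute terms, 0.38 × 8 ≈ 3.0 to 0.54 × 8 ≈ 4.3 mL/min remains at 4 years, in the correct direction. Section 8.2.2 now expects the study to last about 10 years, which gives truncation longer to act.

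**5. Formula choice.** Using the Appendix 3 equations with non-African-American patients and heights of 162 cm (women) and 175 cm (men):

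- Man of 30, creatinine 300 µmol/L: ideal weight 0.9 × 175 − 88 = 69.5 kg. Cockcroft-Gault (140 − 30) × 69.5 / (0.81 × 300) = 31.5. MDRD 186.3 × (300 × 0.0113)^−1.154 × 30^−0.203 = 22.8. Ratio 1.38.
- Woman of 85, creatinine 200 µmol/L: ideal weight 0.9 × 162 − 92 = 53.8 kg. Cockcroft-Gault 0.85 × 55 × 53.8 / (0.81 × 200) = 15.5. MDRD 21.9. Ratio 0.71.
- Ages 60–75 at 200–300 µmol/L: ratios 0.82–1.15.

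Within one patient on one formula the effect on change is small. A rise from 200 to 300 µmol/L gives 200/300 − 1 = −33% (Cockcroft-Gault) and 1.5^−1.154 − 1 = −37% (MDRD). The protocol does not, however, require the formula to stay the same for a patient, as section 5.4.1 does for blood pressure technique.

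**6. What the dialysis form could show.** Assume a start rate r of 5–20% per year, no dropout or competing death, and entry spread over 2.5 years. Expected starts are 560 × the mean of 1 − exp(−r·u), with u uniform from T − 2.5 to T: 72–234 at 4 years and 198–462 at 10 years. For a hazard ratio of 1.5 at two-sided 0.05, power is Φ(√D × ln 1.5 / 2 − 1.96): 0.40–0.87 and 0.81–0.99. The form would hold useful information.

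**The case against.** The strongest reply is that the protocol has other routes to the same information. The general rule in 7.1.1, the laboratory rule in 7.1.3 and serious-event reporting in 7.2.1 can each bring renal decline into the safety record, and section 4.3.3 captures GFR when dialysis is required. All of that is correct. It limits the point to inconsistent rules and incomplete tables. It does not settle which AE rule a site should follow, and 8.2.6 does not say how the off-schedule GFR value enters the summary.

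A reader might infer that dialysis is barred from the AE record, or that worsening counts only if it is unusually fast. The text does not support either: the procedure goes in the treatment section of the AE form when the worsening is recorded, and the other routes exist. A reader might also infer that a drug effect would be masked. The illustrated GFR comparison shrinks but keeps its direction, the slopes are assumed and the assumed drug effects are large, and the database retains the dialysis start.

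It is also fair that renal progression is neither an objective nor an endpoint, and that formula choice has not been shown to differ by arm. If each patient stays on one formula, it adds noise rather than arm bias. That limits the priority of the point but not the case for a nearly costless correction.

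**Conclusion.** The concern holds in a limited form. For about 560 patients, the AE rules contradict each other on worsening that leads to dialysis, the GFR summary is truncated by the outcome it is meant to show, its values may mix formulas and units, and no planned analysis uses the dialysis form. An arm difference in renal decline could be attenuated or obscured in the reported tables.

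No size can be taken from the documents. The 37–54% kept at 4 years rests on the assumed baseline GFR, slopes and dialysis threshold, and the equal AE counts rest on assumed start rates and labelling shares. The composite of death, MI and stroke is untouched. This is a worthwhile, inexpensive improvement to a secondary part of the safety reporting, not a flaw in the main result.

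**What to change.** 1. **Section 8.2.6.** For patients not on dialysis at baseline, add a descriptive by-arm summary of first dialysis start from the existing form: number, rate per 100 patient-years, and cumulative incidence with death as a competing event. Show GFR change beside it, including the value determined when dialysis is required (section 4.3.3).
2. **GFR.** Compute it for every patient with one formula, the abbreviated MDRD that Appendix 3 prefers, from creatinine and demographics already collected. This does not cure differences in creatinine calibration between local laboratories, which Appendix 3 already asks the sponsor to note.
3. **Sections 7.1.1 and 7.1.3.** Reconcile the recording rules so that renal worsening leading to dialysis is recorded alike in both arms, either by defining the criterion or by removing the discretion. Leave serious-event reporting under 7.2.1 intact. The dialysis form should not become the only record of progression, since that would remove the AE assessment of intensity, causality and seriousness.

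The cost is protocol and analysis-plan wording and one or two extra descriptive tables, labelled as not controlled for multiplicity. No new visits, samples or patients are needed.
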